### 10.2 Statistical methods

Demographics and laboratory data will be plotted (e.g. box plots) and summarized by treatment group. Frequency distributions will be used to describe categorical values and basic summary statistics (mean, standard deviation, median, and inter-quartile range) used to describe continuous values. All tests will be two-sided with alpha level 0.05. For quantitative endpoints (e.g. change in kidney and liver volumes, renal function, and SF-36 scales) the two-group independent samples t-test will be used to test for an effect of treatment. Should the assumptions of normality and equality of variances be untenable, we will consider a data transformation or use of the Wilcoxon rank sum test. Both point estimates (mean) and 95% confidence intervals will be used to summarize treatment effects. For qualitative endpoints (e.g. presence or absence of response) we will compare treatment groups using the chi-square or Fisher's exact test as appropriate.

**Efficacy (Liver & kidney):** The primary analysis of treatment efficacy will follow intent-to-treat principles, attempting to include all randomized patients. For the primary endpoint (change in

liver volume) we will not be able to include anyone without a 12 month MRI (kidney volumes will be handled in the same way). For the “response” endpoints, those without a 12 month MRI will be included in the analysis as non-responders. Secondary analysis – Efficacy (QOL): We will have up to 5 longitudinal assessments of QOL for each patient. Repeated measures analysis of variance will be used to compare mean QOL profiles over time between treatment groups. Also, within patient rates of change or slopes in QOL measures will be estimated (using simple linear regression) and compared between groups using the two-sample t-test.

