**Secondary analysis–Kidney volume will be measured as part of the efficacy analysis:**

AEs (both patient and event counts) will be tabulated by organ system (neuro, GI, etc.), individually, by severity and, for each severity, by investigator-assessed relationship to study drug. Fisher’s exact test will be used to compare treatment groups regarding adverse events. Patients who received at least one dose of the randomized study drug will be included.

**Statistical power:** The primary endpoint is one year percentage change in liver volume. Prior data in untreated patients suggest a growth rate (SD) of 5(±3) % per year. We have planned a 2:1 randomization in order to allow as many patients as possible to receive SOM230. The goal is to detect up to a 7.3% percentage point decrease in the mean cyst growth using SOM230 LAR® Depot. With **15 placebo and 30 SOM230** patients, the study will have 80% power (alpha=.05, two-sided) to detect a 7 percentage point difference. To allow for dropouts (1 placebo and 2 SOM230 patients without endpoint data); the study will randomize 16 placebo and 32 SOM230 patients. For any quantitative endpoint the study is powered to detect a difference in treatment means of at least one standard deviation. Secondary endpoints include comparison of responder rates (based on liver and renal growth) and adverse event rates between the two groups. With 16 and 32 patients, a true placebo response (or adverse event rate) of 8 % (1 of 13) vs. 30, 40, or 50% for SOM230 can be detected with 45%, 70%, and 88% power, respectively.

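### The printed 45/70/88% power overstates all three adverse-event figures under Fisher's exact test (35/62/84%); for response by chi-square, only the 45% is clearly wrong

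*Combined protocol and SAP*

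**What the plan says.** The power paragraph of section 10.2 closes with the binary endpoints, which are responder rates based on liver and renal growth, and adverse event rates. For 16 and 32 patients it takes "a true placebo response (or adverse event rate) of 8 % (1 of 13) vs. 30, 40, or 50% for SOM230" and says that these differences "can be detected with 45%, 70%, and 88% power, respectively". One set of three figures serves all of these endpoints. The method or software behind them is not named.

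The group sizes come from the same paragraph: "To allow for dropouts (1 placebo and 2 SOM230 patients without endpoint data); the study will randomize 16 placebo and 32 SOM230 patients".

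The tests are fixed elsewhere in section 10.2, where all tests are two-sided at 0.05:

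- Response: "For qualitative endpoints (e.g. presence or absence of response) we will compare treatment groups using the chi-square" or Fisher's exact test, as appropriate.
- Adverse events: Fisher's "exact test will be used to compare treatment groups regarding adverse events". Section 8 names the same test for year 1 and offers no alternative.

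For the response endpoints, "those without a 12 month MRI will be included in the analysis as non-responders".

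**The concern.** Everything needed to check the sentence is in the text: group sizes, rates, alpha, sidedness and tests. The three figures should therefore follow from a planned test at 16 and 32, and as a set they do not.

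Adverse events are part of the primary objectives in section 3.1, and this is the only power statement the plan makes for comparing them. Someone reading a non-significant 8% versus 30% comparison would credit it with 45% power when the named test has about 35%. The comparison would look more reassuring than it is. What is at stake is interpretation of the adverse-event and secondary response comparisons, not the size of the trial.

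**Working it through.** **Inputs.** Placebo n = 16 and SOM230 n = 32; placebo rate 8%, with 1/13 = 7.7% as a check; SOM230 rates 30, 40 and 50%; two-sided alpha 0.05 (all section 10.2). The group sizes suit both endpoints. Patients without a 12-month MRI stay in the response analysis as non-responders, and the adverse-event analysis takes everyone who received at least one dose.

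**Method.** Let x be the number of events on placebo and y the number on SOM230. There are 17 × 33 possible tables. Exact power is the total probability of the tables where the test rejects:

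Power = Σ Bin(x; 16, p₁) × Bin(y; 32, p₂), over all (x, y) with two-sided p ≤ 0.05.

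**Worked case, 8% versus 30%.** The terms with a higher rate on SOM230 carry essentially all of the power.

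| x on placebo | P(x) | Fisher rejects from y = | P(y that high) | Chi-square rejects from y = | P(y that high) |
|---|---|---|---|---|---|
| 0 | 0.2634 | 8 | 0.7882 | 7 | 0.8869 |
| 1 | 0.3665 | 11 | 0.3560 | 11 | 0.3560 |
| 2 | 0.2390 | 15 | 0.0327 | 13 | 0.1326 |
| 3 | 0.0970 | 17 | 0.0052 | 16 | 0.0138 |

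- Fisher: 0.2076 + 0.1305 + 0.0078 + 0.0005 = 0.346.
- Chi-square: 0.2336 + 0.1305 + 0.0317 + 0.0013 = 0.397.

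**All three scenarios at 16 and 32.**

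| | 30% | 40% | 50% |
|---|---|---|---|
| Printed in the plan | 45% | 70% | 88% |
| Fisher's exact, 8% | 34.6% | 62.2% | 83.5% |
| Printed minus Fisher (points) | 10.4 | 7.8 | 4.5 |
| Chi-square, 8% | 39.7% | 69.8% | 89.8% |
| Printed minus chi-square (points) | 5.3 | 0.2 | −1.8 |
| Fisher's exact, 1/13 | 35.9% | 63.6% | 84.5% |
| Chi-square, 1/13 | 41.0% | 71.1% | 90.5% |

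Neither planned test gives the printed set. Rounding of 1 in 13 to 8% moves the results by about 1 point or less and does not explain the gap.

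**A mixed rule for response.** The plan does not define when each test is appropriate. Suppose Fisher's test replaces chi-square whenever an expected count is below 5 (an assumption). Power is then 37.1/69.4/89.8%, and the 45% is still not reached. At the design rates the smallest expected count is the placebo one, 16 × (16 × 0.08 + 32 × p₂)/48, which is 3.6, 4.7 and 5.8. Under that convention the first two scenarios would usually go to Fisher's test.

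**The case against.** The best defence is that chi-square is a planned test for response. At 16 and 32 it gives 69.8% and 89.8%, so the printed 70% and 88% hold within 2 points and the 88% is slightly cautious. This stands. It limits the response part of the point to the 45%. It does not help with adverse events, where only Fisher's test is named, and it does not rescue the 45%.

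A second defence is that power sections often use approximate formulas, and that differences of this size are typical of them. That may explain the figures but does not make them right for the tests that will be run. A reader might infer a particular cause, for example that the evaluable 15 and 30 were used, or that the arms were swapped. The documents do not support choosing one. Several unrelated methods and settings come within 2 points of all three figures, and the plan names none.

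A reader might also go further and say that the 8% versus 30 to 50% grid is wrong for the liver responder, who is defined in section 7.4.1.1 by growth below 2%, and that other rates should replace it. The documents do not support that as an error. The grid is conditional and is shared by liver response, renal response and adverse events. Replacement rates would need a normal distribution that the plan does not state. They would also need an SD inferred backwards from the primary power claim, and a sign for the prior placebo change that section 1.5.2.2 leaves unclear: it gives 0.92% beside volumes that fall from 5374 to 5361 ml.

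**Conclusion.** The point holds in a limited form. For adverse events, all three printed figures are too high: 45/70/88% against 35/62/84% by the named test. For response, the 45% is too high under either planned test (40% by chi-square, 35% by Fisher). The 70% and 88% are adequate by chi-square and overstated only if Fisher's test is used. To read it as all three figures being wrong for every endpoint would go too far.

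The result rests on the plan's own sizes, rates, alpha and tests, on independent binomial counts in each arm, and on full groups of 16 and 32. It says nothing against the sample size, which is set by the percentage change in liver volume, and it leaves the primary analysis, type I error and conduct untouched. Severity: minor.

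**What to change.** Rewrite the last sentence of the power paragraph in section 10.2:

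- Name the test, and state that power is exact, two-sided at 0.05, with 16 and 32 patients.
- For adverse events, print 35%, 62% and 84% (Fisher's exact test) for 8% versus 30, 40 and 50%.
- For response, print 40%, 70% and 90% if chi-square is used, or 35%, 62% and 84% if Fisher's test is used.

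The cost is the wording of one sentence. Printed adverse-event power falls by about 10, 8 and 4 to 5 points.

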## 12 Appendices

### 12.1 Appendix 1 Guidance for diarrhea management

General recommendations:

- Stop all lactose-containing products, alcohol
- Stop laxatives, bulk fiber (Metamucil, Procter & Gamble), and stool softeners (docusate sodium; Colace, Roberts)
- Drink 8 to 10 large glasses of clear liquids per day (water, Pedialyte (Ross), Gatorade (Quaker), broth)
- Eat frequent small meals (bananas, rice, applesauce, Ensure, toast)
- Stop high-osmolar food supplements such as Ensure Plus and Jevity Plus (with fiber)

It is recommended that patients be provided loperamide tablets. It is mandatory that patients are instructed on the use of loperamide in order to manage signs or symptoms of diarrhea at home. Patients should be instructed to start oral loperamide (initial administration of 4mg, then 2mg every 4 hours -maximum of 16 mg/day) at the first sign of loose stool or symptoms of abdominal pain. These instructions should be provided during each office visit and the site should ensure that the patient understood the instruction. At the beginning of treatment, each patient should be specifically questioned regarding any experience of diarrhea or diarrhea related symptoms. If symptoms were experienced, then the site should question the patient regarding the actions taken for these symptoms.

#### Treatment of diarrhea grade 1 or 2

Diarrhea grade 1 or 2 will be treated with standard loperamide (initial at first administration 4 mg, then 2 mg every 4 hours (maximum of 16 mg/day) or after each unformed stool).

#### 12-24 hours later:

##### Diarrhea resolved

- Continue instructions for dietary modification
- Gradually add solid foods to diet
- Discontinue loperamide after 12-hours diarrhea-free interval

##### Diarrhea unresolved

Persisting diarrhea grade 1 or 2 will be treated with addition of opium tincture or dihydrocodeine tartrate tablets/injections with monitoring of patients condition to rule out dehydration, sepsis, ileus) medical check and selected workup if patient does not need hospitalization (see section Diarrhea workup and additional test in the particular trial protocol). Observe patient for response to antidiarrheal treatment.

Persisting diarrhea grade 3 or 4 may be treated with hospitalization, high dose loperamide (initial 4 mg, then 2 mg every 2 hours) and addition of opium tincture or dihydrocodeine tartrate tab-

lets/injections, start of IV fluids and antibiotics as needed with monitoring of patients condition (to rule out dehydration, sepsis, ileus) medical check and workup (perform appropriate additional testing). Observe patient for response.

**After 24 hours:****Diarrhea resolved**

- Continue instructions for dietary modification
- Gradually add solid foods to diet
- Discontinue loperamide and/or other treatment after 12-hours diarrhea-free interval

**Diarrhea unresolved**

- If diarrhea still persisting (NCI CTC grades 1 and 2), after 2x 24 hours with high dose loperamide and opiates then admit to hospital and employ measures as for grade 3 and 4 until diarrhea resolved
- If diarrhea still persisting and progressed to NCI grades 3 and 4, employ measures described below.

**Treatment of diarrhea grade 3 or 4**

Severe diarrhea grade 3 or 4 may be treated with hospitalization, high dose loperamide (initial 4 mg, then 2 mg every 2 hours and addition of opium tincture or dihydrocodeine tartrate tablets/injections, start of IV fluids and antibiotics as needed with monitoring of patients condition (to rule out dehydration, sepsis, ileus) medical check and workup (see section Diarrhea workup and additional test in the particular trial protocol). Observe patient for response.

**After 24 hours:**

- If diarrhea persisting administer SQ Sandostatin/octreotide (100-500 µg tid)
- Continue IV fluids and antibiotics as needed
- If diarrhea grade 3 or 4 still persists patients should receive opium tincture or dihydrocodeine tartrate injections SQ or IM
- If diarrhea grade 3 or 4 is still persisting SQ Sandostatin/octreotide (500-1000 µg tid) should be administered.
- To control and/or resolve diarrhea, next cycle of treatment should be delayed by 1 or 2 weeks. Treatment should be continued only when diarrhea resolved.

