## 6.5 Pasireotide LAR dose adjustment

We will use the oncology dosing (including NETs) as already described above, pasireotide LAR at 60 mg every 28 days being the recommended starting dose for oncological indications. If tolerability issues occur, the treatment dose may be reduced to pasireotide LAR at 40 mg with next scheduled injection. Patients requiring a dose reduction can return to the higher dose once the tolerability issue is resolved. However, patients not able to tolerate the minimum pasireotide LAR dose of 20 mg are recommended to be discontinued from study.

All dose changes must be recorded on the Dosage Administration Record CRF. Table 7 outlines the dose reduction steps for pasireotide.

Emergency un-blinding will be done at the discretion of the Principal Investigator [REDACTED] in cases where she feels it is necessary for the safety of the patient.

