### 6.5.1 Permitted study drug adjustments

Toxicity will be assessed using the NCI-CTC for Adverse Events, version 3.0 (CTCAEv3.0, <http://ctep.cancer.gov/forms/CTCAEv3.pdf>). For patients who are unable to tolerate the protocol-specified SOM230C dosing schedule, dose-adjustment guidelines are given below.

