## 6.6 Pasireotide LAR / placebo dose adjustment

As already described above, pasireotide LAR/placebo at 60 mg every 28 days is the recommended starting dose for oncological indications (including NETs). If tolerability issues occur, the treatment dose may be reduced to pasireotide LAR at 40 mg with next scheduled injection. Patients requiring a dose reduction can return to the higher dose once the tolerability issue is resolved. However, patients not able to tolerate the minimum pasireotide LAR dose of 20 mg are recommended to be discontinued from study.

All dose changes must be recorded on the Dosage Administration Record CRF. Table 7 outlines the dose reduction steps for pasireotide.

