**Pancreatic****Pancreatitis**

Grade 1	Maintain dose level
---------	---------------------

Grade 2	Maintain dose level
Grade 3	Omit dose and discontinue patient from study treatment
Grade 4	Omit dose and discontinue patient from study treatment
Amylase and/or lipase	
Grade 1 (> ULN - 1.5 x ULN)	Maintain dose level
Grade 2 (> 1.5 - 2.0 x ULN)	Maintain dose level
Grade 3 (> 2.0 - 5.0 x ULN)	For asymptomatic: Omit dose until resolved to ≤ Grade 1, then 
 
• If resolved ≤ 7 days, then maintain dose level
 
• If resolved > 7 days, then ↓ 1 dose level
 
 For symptomatic: Omit dose and discontinue patient from study treatment
Grade 4 (> 5.0 x ULN)	Omit dose and discontinue patient from study treatment A CT scan or other imaging study to assess the pancreas, liver and gallbladder must be performed within 1 week of the first occurrence of any ≥ CTCAE grade 3 of amylase and/or lipase.
Endocrine/metabolic	
Fasting plasma glucose (FPG) or 2-hour postprandial capillary glucose (PPG)	
FPG <126 mg/dL or PPG < 140 mg/dL	Maintain dose level
Grade 1 (> ULN – 160 mg/dL)	appendix 2 section 12.2.
Grade 2 (> 160 – 250 mg/dL)	appendix 2 section 12.2.
Grade 3 (> 250 – 500 mg/dL)	appendix 2 section 12.2.
Grade 4 (> 500 mg/dL)	appendix 2 section 12.2.
Cardiac	
Cardiac - prolonged QTc interval	

 
• QTcF > 480 ms and ≤ 500 ms
 
• QTcF > 500 msec
 
	
If at any time a QTcF > 480 ms and ≤ 500 ms is observed a cardiology consultation must be sought to re-evaluate the abnormal ECG finding.
 
 
1. Triplicate ECGs (2-3 minutes apart) need to be taken approximately 1 hour after the initial ECG.
 
2. If the mean QTcF is > 500 ms, the patient must postpone study treatment until a cardiologist has re-evaluated the ECG.
 
3. The re-evaluation of ECG needs to be done as soon as practical but within 7 days of the initial abnormal ECG.
 
4. If the cardiologist confirms a mean QTcF > 500 ms, the patient must be discontinued.
 

Cardiac general	
Grade 1 or 2	Maintain dose level
Grade 3	Omit dose until resolved to ≤ Grade 1, then ↓ 1 dose level
Grade 4	Omit dose and discontinue patient from study treatment
Other adverse events	
Grade 1 or 2	Maintain dose level
Grade 3	Omit dose until resolved to ≤ Grade 1, then ↓ 1 dose level

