Grade 4	Omit dose and discontinue patient from study treatment
Detailed treatment guidance on QT prolongation, hyperglycemia and diarrhea will be provided as appendices of the protocol	

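### For grade 4 diarrhea, Table 7 recommends stopping study drug while Appendix 1 delays the next injection and allows it to continue, and no text says which prevails

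*Combined protocol and SAP*

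**What the plan says.** Dose changes are set out in Sections 6.5 and 6.6 and in Table 7. Both sections state that "Table 7 outlines the dose reduction steps for pasireotide", and Section 6.5.1 adds that "dose-adjustment guidelines are given below". Table 7 names neutropenia, liver tests, glucose, QTc and other specific toxicities, but not diarrhea. Diarrhea therefore falls under the final category, other adverse events. At grade 3 that category says "Omit dose until resolved to ≤ Grade 1, then ↓ 1 dose level"; at grade 4 it says "Omit dose and discontinue patient from study treatment". The table presents all of these as recommended modifications.

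A note at the end of Table 7 points the reader to the appendices for fuller guidance on three topics, one of which is diarrhea. Appendix 1 (Section 12.1) treats the two highest grades together: "Severe diarrhea grade 3 or 4 may be treated with hospitalization, high dose loperamide". Persistent grade 1 or 2 diarrhea is also routed there, with the instruction to "admit to hospital and employ measures as for grade 3 and 4 until diarrhea resolved". The only study-drug instruction in that block is the last bullet, whose stated purpose is to bring the diarrhea under control: the "next cycle of treatment should be delayed by 1 or 2 weeks. Treatment should be continued only when diarrhea resolved". It does not separate grade 3 from grade 4, does not mention discontinuation and does not refer back to Table 7.

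**The concern.** At grade 4 the two texts lead to different actions. Under Table 7 there is no next cycle. Under Appendix 1 the next cycle is postponed by a week or two and may go ahead once the diarrhea has cleared. A clinician who follows Table 7's own pointer to the diarrhea appendix reaches a rule without the stop. Appendices 3 and 4 each list discontinuation criteria for their topic, so the absence of any in Appendix 1 could be read as meaning that diarrhea has no stop rule.

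What is at stake is patient safety and uniform conduct. Pasireotide LAR is a depot; Section 1.5.1.1.1 describes release for up to 42 days after a single injection in healthy volunteers. An injection given in error could not be withdrawn quickly. The same is true of any restart of this drug, so it explains why the conflict is worth removing but does not enlarge it.

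**Working it through.** No figure in the plan depends on this point, so the main check is to set the texts side by side.

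| Situation | Table 7, other adverse events | Appendix 1 | Compatible? |
|---|---|---|---|
| Grade 1–2, persistent | Keep the dose level | Manage as for grade 3 or 4; delay until resolved | Yes: one sets dose, the other timing |
| Grade 3 | Hold to grade 1 or lower, then one level down | Delay 1–2 weeks; continue only when resolved; no dose given | Yes: Table 7 gives the dose, Appendix 1 the stricter restart condition |
| Grade 4 | Hold and discontinue | Delay 1–2 weeks; continue only when resolved | No |

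Next, does any other text settle the grade 4 row?

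- Sections 6.5, 6.5.1 and 6.6 favour Table 7 as the dosing source, but none addresses diarrhea or ranks the table above the appendix.
- Section 6.6 also says that, for tolerability, "the treatment dose may be reduced to pasireotide LAR at 40 mg with next scheduled injection". This is permissive and does not depend on grade.
- Section 6.8 requires discontinuation for listed findings, none of which names diarrhea, and otherwise leaves adverse events to the investigator's judgment.

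So the conflict remains.

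**How many patients.** Section 1.5.1.1 describes earlier LAR data by dose group (20, 40, 60 mg): acromegaly 10 + 12 + 13 = 35 patients, carcinoid 12 + 14 + 16 = 42, total 77. Carcinoid diarrhea was grade 1 or 2 apart from one grade 3 event. For acromegaly the text says mostly grade 1 and none serious. Reading that as no grade 4 is an inference: grade 4 is taken as life-threatening, and Section 7.5.1 counts life-threatening events as serious.

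With zero events in n patients, the exact one-sided 95% upper limit is 1 − 0.05^(1/n). It is multiplied by 48 because up to 48 patients may receive active drug over the three years.

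- All doses, n = 77: 1 − 0.05^(1/77) = 3.82%; × 48 = 1.8 patients.
- 60 mg only, this trial's starting dose (Section 6.1.4), n = 13 + 16 = 29: 1 − 0.05^(1/29) = 9.81%; × 48 = 4.7 patients.
- Carcinoid only, where grades are stated outright, n = 42: 1 − 0.05^(1/42) = 6.88%; × 48 = 3.3 patients.

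The observed count is zero in each case. The higher limits reflect smaller denominators and are not evidence of greater risk.

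**The case against.** The best defence is that the two texts do different jobs. Appendix 1 is symptom guidance (diet, loperamide, opiates, fluids, octreotide, work-up), while Table 7 is the named source for dosing. Where the protocol wants an appendix to govern dosing it says so: the glucose rows of Table 7 refer to Appendix 2, and no row does this for diarrhea. The Appendix 1 bullet can also be read as setting a condition for patients still eligible for another cycle, without ordering one after grade 4. On that reading Table 7 simply prevails.

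This is a plausible harmonisation, and probably what was intended, but it is not written down for diarrhea. The bullet sits under a heading that includes grade 4, and telling a reader to delay the next cycle presupposes that there will be one. Appendix 1 also refers to a work-up section in the particular trial's protocol, which suggests general text not reconciled with this trial's table.

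The practical safeguards do stand. Injections are given in the clinic at a single center, dose changes must be recorded, and Section 6.8 requires stopping if the investigator finds a significant safety risk. A life-threatening event would be reported as serious within 24 hours, and a safety committee meets every six months. Re-injection without thought after such an event is unlikely.

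A reader might also infer that the protocol gives no restart dose after grade 3. It does: Table 7 specifies one level down. The silence of Appendix 1 there is an omission that Table 7 fills, so it is not a second conflict.

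**Conclusion.** The point holds for grade 4 diarrhea only. Two study-drug instructions conflict and nothing in the protocol ranks them. It is a minor safety-consistency matter. No grade 4 diarrhea is reported in the LAR data the protocol summarises, and the upper limits run from 1.8 to 4.7 of 48 patients depending on which earlier groups are counted. Those limits assume that the acromegaly patients had no grade 4 events and that rates carry over to this population. Exposure per patient in the earlier study is not given, although glucose events up to day 1131 show that some follow-up was long.

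Three stronger readings are not supported. Table 7 recommends discontinuation; its wording does not make it mandatory. Appendix 1 allows continuation after resolution; it does not oblige anyone to re-inject. And nothing here bears on the liver-volume endpoint, the sample size or the power statement.

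**What to change.** In Appendix 1, limit the delay-until-resolved bullet to grade 3 diarrhea and to persistent grade 1–2 diarrhea managed in that block, and add after it: *For grade 4 diarrhea, discontinue study treatment per Table 7.*

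A pointer to Table 7 for the grade 3 restart dose is optional. If one is added, it should say that restart is one dose level lower and only once diarrhea has resolved. Otherwise Table 7's threshold of grade 1 or lower would sit beside the appendix's stricter condition and create a new mismatch.

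The cost is one edited bullet and one added sentence, handled as a written amendment under Section 9. Table 7, visits, sample size and analysis are unchanged.
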